## **12.3. Administrative Procedures**

### **12.1.1      Informed Consent**

The Investigator must obtain documented consent from each potential subject or each subject's legally acceptable representative prior to participating in a clinical trial.

Consent must be documented by the subject's dated signature or by the subject's legally acceptable representative's dated signature on a consent form along with the dated signature of the person conducting the consent discussion. A copy of the signed and dated consent form should be given to the subject before participation in the trial.

The initial informed consent form, any subsequent revised written informed consent form and any written information provided to the subject must receive the IRB/ERC's approval/ favorable opinion in advance of use. The subject or his/her legally acceptable representative should be informed in a timely manner if new information becomes available that may be relevant to the subject's willingness to continue participation in the trial. The communication of this information will be provided and documented via a revised consent form or addendum to the original consent form that captures the subject's dated signature or by the subject's legally acceptable representative's dated signature.

The informed consent will adhere to IRB/ERC requirements, applicable state laws and federal regulations.

### **12.1.2    Inclusion/Exclusion Criteria**

All inclusion and exclusion criteria will be reviewed by the investigator or qualified designee to ensure that the subject qualifies for the trial.

### **12.1.3    Medical History**

A medical history will be obtained by the investigator or qualified designee. Medical history will include all active conditions, and any condition diagnosed within the prior 10 years that are considered to be clinically significant by the Investigator. Details regarding the disease for which the subject has enrolled in this study will be recorded separately and not listed as medical history.

### **12.1.4    Prior and Concomitant Medications**

#### **12.1.4.1    Prior Medications**

The investigator or qualified designee will review prior medication use, including any protocol-

specified washout requirement, and record prior medication taken by the subject within 28 days before starting the trial. Treatment for the disease for which the subject has enrolled in this study will be recorded separately and not listed as a prior medication.

#### **12.1.4.2 Concomitant Medications**

The investigator or qualified designee will record medication, if any, taken by the subject during the trial. All medications related to reportable SAEs and ECIs should be recorded.

### **12.1.5 Disease Details and Treatments**

#### **12.1.5.1 Disease Details**

The investigator or qualified designee will obtain prior and current details regarding disease status.

#### **12.1.5.2 Prior Treatment Details**

The investigator or qualified designee will review all prior cancer treatments including systemic treatments, radiation and surgeries.

#### **12.1.5.3 Subsequent Anti-Cancer Therapy Status**

The investigator or qualified designee will review all new anti-neoplastic therapy initiated after the last dose of trial treatment. If a subject initiates a new anti-cancer therapy within 30 days after the last dose of trial treatment, the 30 day Safety Follow-up visit must occur before the first dose of the new therapy. Once new anti-cancer therapy has been initiated the subject will move into survival follow-up.

### **12.1.6 Clinical Procedures/Assessments**

#### **12.1.6.1 Adverse Event (AE) Monitoring**

The investigator or qualified designee will assess each subject to evaluate for potential new or worsening AEs as specified in the [Trial Flow Chart](#) and more frequently if clinically indicated. Adverse experiences will be graded and recorded throughout the study and during the follow-up period according to NCI CTCAE Version 4.0. Toxicities will be characterized in terms regarding seriousness, causality, toxicity grading, and action taken with regard to trial treatment.

Refer to [Section 10](#) for detailed information regarding the assessment and recording of adverse events.

#### **12.1.6.2 Physical Exam**

The investigator or qualified designee will perform a complete physical exam during the screening period. Clinically significant abnormal findings should be recorded as medical history. A physical exam should be performed as specified in the [Trial Flow Chart \(Section 12.1\)](#). For subsequent cycles the investigator or qualified designee will perform a directed physical exam as clinically indicated prior to dosing on Day 1 of each treatment cycle. After the first dose of trial treatment new clinically significant abnormal findings should be recorded as AEs.

#### **12.1.6.3 Vital Signs**

The investigator or qualified designee will take vital signs at screening, prior to the

administration of each dose of trial treatment and at treatment discontinuation as specified in the

[Trial Flow Chart \(Section 12.1\)](#). Vital signs should include temperature, pulse, respiratory rate, weight and blood pressure. Height will be measured at screening only.

**12.1.6.4                    Eastern Cooperative Oncology Group (ECOG) Performance Status**

The investigator or qualified designee will assess ECOG status (see [Appendix 1](#)) at screening, prior to the administration of each dose of trial treatment and discontinuation of trial treatment as specified in the Trial Flow Chart.

**12.1.6.5                    Tumor Imaging and Assessment of Disease**

CT chest, abdomen, and pelvis with contrast will be performed at baseline screening, prior to the administration of study drugs, and every 8 weeks thereafter.

**12.1.6.6                    Tumor Tissue Collection and Correlative Studies Blood Sampling**

All patients will have tumor biopsy specimens obtained at baseline prior to study drug administration and then during week 8 to assess methylation status and immune response. Peripheral blood will be evaluated for methylation status at baseline and then prior to treatment administration on weeks 3, 5, and 6.

**12.1.6.7                    Laboratory Procedures/Assessments**

Details regarding specific laboratory procedures/assessments to be performed in this trial are provided below. Laboratory tests for hematology, chemistry, urinalysis, and others are specified in the [Trial Flow Chart](#) (Section 12.1).

Laboratory tests for screening should be performed within 7 days prior to the first dose of treatment. After Cycle 1, pre-dose laboratory procedures can be conducted up to 72 hours prior to dosing. Results must be reviewed by the investigator or qualified designee and found to be acceptable prior to each dose of trial treatment.

## **13.                    MEASUREMENT OF EFFECT**

### **13.1. Antitumor Effect – Solid Tumors**

For the purposes of this study, patients should be re-evaluated for response every 8 weeks. In addition to a baseline scan, confirmatory scans should also be obtained 8 (not less than 4) weeks following initial documentation of objective response.

Response and progression will be evaluated in this study using the new international criteria proposed by the revised Response Evaluation Criteria in Solid Tumors (RECIST) guideline (version 1.1). Changes in the largest diameter (unidimensional measurement) of the tumor lesions and the shortest diameter in the case of malignant lymph nodes are used in the RECIST criteria.

### **13.1.1 Definitions of evaluable subjects**

Evaluable for toxicity: All patients will be evaluable for toxicity from the time of their first treatment with azacitidine.

Evaluable for DLT assessment: The initial 6 subjects treated with at least 1 cycles (5 doses) of azacitidine and 1 dose of pembrolizumab will be evaluated for DLT. Subjects who do not complete these doses will be replaced.

Evaluable for PFS- primary outcome: All subjects who receive a single dose of pembrolizumab will be included in the primary outcome analysis of PFS. If subjects are removed from study prior to completing a single dose of pembrolizumab, they will be replaced.

Evaluable for objective response: Only those patients who have measurable disease present at baseline, have received at least one cycle of therapy, and have had their disease re-evaluated will be considered evaluable for response. These patients will have their response classified according to the definitions stated below. (Note: Patients who exhibit objective disease progression prior to the end of cycle 1 will also be considered evaluable.)

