### 1.1. Trial Design Overview

This is a single-arm, single-center, open-label trial of azacitidine combined with pembrolizumab in subjects with locally-advanced or metastatic pancreatic adenocarcinoma. Thirty-one evaluable subjects will be enrolled to assess the efficacy and safety of combination therapy in the second- line setting.

All subjects will have received systemic first-line chemotherapy, 5-FU or gemcitabine-based combination or monotherapy, prior to enrollment on the study. Azacitidine daily for 5 days will be given every 4 weeks (28 days). Fixed-dose pembrolizumab will be administered every 3 weeks for up to approximately 2 years beginning 2 weeks after initiation of azacitidine. The primary efficacy endpoint will be progression-free survival among all enrolled subjects. Disease progression will be determined based on RECIST 1.1 criteria; however, patients will be permitted to continue therapy following the development of progression of disease by RECIST 1.1 criteria if considered clinically appropriate by the study principal investigator.

As preliminary data suggests there is minimal toxicity overlap between pembrolizumab and a hypomethylating agent, there will be an accelerated Phase 1 dose determination component of the study. In the initial cohort, low-dose azacitidine will be administered, as studied in patients with advanced or metastatic solid tumors, and pembrolizumab will be administered at fixed dose

as detailed in the protocol. An initial cohort of 6 subjects will be enrolled, treated with combination therapy, and assessed for safety. Following enrollment of the initial 6 evaluable subjects all toxicity data will be reviewed. If 2 or more patients experience a treatment related dose-limiting toxicity (DLT) within the first 6 weeks of treatment administration (Defined in Section 5.2), then accrual at that dose level will stop. We will allow for 1 dose reduction in azacitidine and if agreed by the PI, the study will resume at the lower dose (Dose -1) and will again accrue 6 subjects who will receive combination therapy. If 2 or more subjects experience treatment related DLTs at this level, we will discontinue the combination study.

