### **5.3. Number of Patients**

Thirty-one subjects who are evaluable for progression-free survival will be enrolled. Unevaluable patients (as defined in [Section 13.1.1](#)) will be replaced.

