#### **15.2.3 Efficacy Population**

Evaluable for PFS- primary outcome: All subjects who receive a single dose of protocol therapy will be included in the primary outcome analysis of PFS. If subjects are removed from study prior to completing a single dose of pembrolizumab, they will be replaced but will be included in the primary analysis.

Evaluable for objective response: Only those patients who have measurable disease present at baseline, have received at least one cycle of therapy, and have had their disease re-evaluated

will be considered evaluable for response. These patients will have their response classified according to the definitions stated below. (Note: Patients who exhibit objective disease progression prior to the end of cycle 1 will also be considered evaluable.)

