#### **15.2.4 Reporting of Outcomes**

All conclusions should be based on all eligible patients. Sub analyses may then be performed on the basis of a subset of patients, excluding those for whom major protocol deviations have been identified (e.g., early death due to other reasons, early discontinuation of treatment, major protocol violations, etc.). However, these sub analyses may not serve as the basis for drawing conclusions concerning treatment efficacy, and the reasons for excluding patients from the analysis should be clearly reported. The 95% confidence intervals should also be provided.

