### **15.7. Analysis Populations**

All subjects who received at least one dose of study treatment will be included in the primary and secondary efficacy and safety analysis as detailed in [Section 15.2](#).

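### Section 13.1.1 implies a primary PFS set of pembrolizumab-treated subjects, while 15.2.3 and 15.7 analyse everyone given any protocol therapy

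*Combined protocol and SAP*

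**What the plan says.** Sections 13.1.1 and 15.2.3 use the same label for the PFS-evaluable set and give it different content.

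- **13.1.1:** "All subjects who receive a single dose of pembrolizumab will be included in the primary outcome analysis of PFS". Subjects removed before that dose are replaced. Nothing is said about keeping them in the analysis.
- **5.3:** 31 PFS-evaluable subjects are to be enrolled. The sentence on replacement opens "Unevaluable patients (as defined in" and names Section 13.1.1.
- **15.2.3:** "All subjects who receive a single dose of protocol therapy will be included in the primary outcome analysis of PFS". Of subjects removed before pembrolizumab it says "they will be replaced but will be included in the primary analysis".
- **15.7:** "All subjects who received at least one dose of study treatment will be included in the primary and secondary efficacy and safety analysis", with a reference back to Section 15.2 for the detail.
- **1.1:** "The primary efficacy endpoint will be progression-free survival among all enrolled subjects".
- **15.2.4:** "All conclusions should be based on all eligible patients".

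On timing, 13.6.1.1 counts PFS from the first day of trial treatment, which is azacitidine on week 1 day 1 (12.1, footnote o). Section 1.1 has pembrolizumab "beginning 2 weeks after initiation of azacitidine", and Table 3 places it in week 3.

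**The concern.** A subject who receives azacitidine and then dies before week 3 is in the primary analysis under 15.2.3 and 15.7. Under the natural reading of 13.1.1 with 5.3 the same subject is replaced and left out. No rule says which section prevails, so two analysts could report different primary results from the same data. The sets coincide only if every treated subject reaches pembrolizumab.

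The direction of the error is known. A set that requires a pembrolizumab dose, with the clock started at azacitidine, contains only subjects who stayed on study for about 14 days after time zero (guarantee time). The trial has no control arm and is judged against a fixed 2-month median (15.2.5), so nothing offsets the loss of early failures.

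**Working it through.** **The plan's own figure.** The only figure nearby is N = 31 for 80% power, median 2 versus 4 months, one-sided alpha 0.05, 18 months of accrual plus 6 of follow-up (15.2.5). The Freedman two-arm formula comes close: (1.645 + 0.842)² × (1.5/0.5)² = 55.6, so 56 events. With event probabilities 0.980 and 0.892 (mean 0.936), 56/0.936 = 59.8, or 30 per arm; power at 31 per arm is 81.4%. This figure does not settle who is analysed, because 31 is the accrual target under either set.

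**Inputs from the documents.** Null median 2 months and one-sided alpha 0.05 (15.2.5); 31 subjects to reach pembrolizumab (5.3, 13.1.1); 14 days between time zero and pembrolizumab (1.1, Table 3).

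**Assumptions.** Exponential PFS, with events observed when they happen. A share p of subjects with an event before day 14 is removed and replaced; the documents give no such share. The plan names no test, only a Kaplan-Meier median with 95% interval, so two candidate tests are used.

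**Step 1, events before day 14.** 14/30.4375 = 0.46 months; 1 − 0.5^(0.46/2) = 0.147.

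**Step 2, expected number replaced.** 31 × 0.147p/(1 − 0.147p).

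**Step 3, apparent null median in the 13.1.1 set.** The kept subjects have survival 0.5^(t/2)/(1 − 0.147p) after day 14. Setting this to 0.5 gives t = 2 × [1 − log2(1 − 0.147p)].

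**Step 4, one-sample log-rank.** Reject if (O − E)/√E < −1.645. This was simulated with 200,000 trials per row, enrolling until 31 reach pembrolizumab and analysing each trial with both sets. Repeat runs lie within about 0.2 percentage points.

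**Step 5, exact binomial on PFS status at 2 months.** Reject if 21 or more of 31 are progression-free; P = 0.0354 under 0.5. In the 13.1.1 set the probability per subject becomes 0.5/(1 − 0.147p) = 0.508, 0.519, 0.540.

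| p | Replaced (mean) | Null median, 13.1.1 set | Log-rank error, 13.1.1 set | Log-rank error, 15.2.3 set | Binomial error, 13.1.1 set |
|---|---|---|---|---|---|
| 0% | 0 | 2.00 months | 3.8% | 3.8% | 3.5% |
| 10% | 0.5 | 2.04 months | 4.3% | 3.8% | 4.2% |
| 25% | 1.2 | 2.11 months | 5.4% | 3.8% | 5.5% |
| 50% | 2.5 | 2.22 months | about 7.7% | 3.9% | 8.6% |

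The binomial error in the 15.2.3 set stays at 3.2 to 3.4% across the last three rows.

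**Step 6, removal unrelated to PFS.** If 3, 5 or 10% of all subjects leave before pembrolizumab for reasons such as withdrawn consent, the log-rank error in the 13.1.1 set stays at 3.8%. Only event-related removal matters.

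**Step 7, which row is plausible.** The first scheduled scan is at week 8 (12.1, footnote k), so events recorded before day 14 would be mainly deaths. Assumed survival medians of 8, 6 and 3 months at constant hazard give 3.9, 5.2 and 10.1% dead by day 14, or 1.2, 1.6 and 3.1 of 31. Entry requires ECOG 0 or 1 and a life expectancy above 3 months (6.1), so a constant hazard from day 1 probably overstates this.

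**Step 8, enrolment.** If a share q of treated subjects leaves before pembrolizumab, 31/(1 − q) must be enrolled: 32, 33, 35 or 37 at q = 3, 5, 10 or 15%. Section 15.2.3 analyses all of them; 13.1.1 analyses 31.

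**The case against.** The strongest reply is that the statistical section already answers the question. Section 15.2 is the part on analysis populations, it treats exactly this case, and it keeps the replaced subjects; 15.7 agrees. Section 13.1.1 belongs to the measurement chapter. Its PFS sentence does not limit the set to pembrolizumab-treated subjects in so many words, whereas its next paragraph, on objective response, does use the word *only*. Read alone, the PFS sentence is also true under 15.2.3. All of this stands, and it is why 13.1.1 is said here to imply the narrower set. The implication is still fair: the sentence defines who is evaluable, 5.3 relies on it to name unevaluable patients, and it lacks the retention clause that 15.2.3 contains.

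A reader might count four rival definitions by adding 1.1 and 15.2.4. That is too strong. The reference in 1.1 to all enrolled subjects points toward the inclusive set, and 15.2.4 bars conclusions from subsets that drop early deaths or early discontinuations. They are loose wordings to align.

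A reader might also see a flat contradiction over the ORR and DCR denominator. Section 15.7 puts all treated subjects into the secondary efficacy analysis, but it refers to 15.2 for detail, and 15.2.3 holds the response-evaluable set. Some ambiguity remains. Choosing all treated subjects as the main denominator would be partly a matter of preference.

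On size, the error rates belong to assumed tests and shares. With the first scan at 8 weeks (56/30.4375 = 1.84 months), median shifts of 0.04 or 0.11 months would be hard to see. Clinical deterioration without objective progression is not itself a PFS event, and the calculation does not cover it.

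**Conclusion.** The inconsistency is real and stands in current text. Sections 13.1.1 and 5.3 imply a pembrolizumab-treated primary set; 15.2.3 and 15.7 define an any-therapy set that keeps replaced subjects. Section 15 holds the sounder rule, because it matches the PFS time origin. The harm, an upward bias in PFS and some inflation of type I error, arises only if 13.1.1 is followed.

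The size is unknown from the documents. Under the assumptions above the log-rank error is about 4.3, 5.4 or 7.7% when about 0.5, 1.2 or 2.5 early-event subjects are lost, against about 3.8% in the 15.2.3 set. At the low end, the more likely case, it stays below the nominal 5%.

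A reader might infer a much larger inflation, since removing every subject with an event before day 14 would take the error to about 16%. The documents do not support that as an estimate: with no scheduled scan before week 8, most modelled progressions would not be known by day 14. It is a theoretical bound. Confidence is high in the textual mismatch and low in the amount of bias. It should be corrected before analysis, so that the set is not chosen with the data in view.

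**What to change.** Conform 13.1.1 and 5.3 to 15.2.3. The primary PFS set is all subjects with at least one dose of any protocol therapy, counted from that dose, including replaced subjects. State separately that replacement continues until 31 subjects have received pembrolizumab and affects accrual only. Align the wording in 1.1 and 15.2.4. Note in 6.4 and 15.4 that the totals of 31 and 37 do not count replacements; 37 is the first DLT cohort of 6 plus 31 at the lower dose level.

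Optional: in 13.6.1.2 and 15.2.6.1, name the denominator for ORR and DCR (response-evaluable or all treated) and report the other alongside it. No success threshold depends on these rates.

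The cost is a wording amendment. The analysed number may slightly exceed 31, and the PFS estimate may be slightly less favourable.

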## **13.2. Disease Parameters**

Measurable disease: Measurable lesions are defined as those that can be accurately measured in at least one dimension (longest diameter to be recorded for non-nodal lesions and short axis for nodal lesions) as  $\geq 20$  mm by chest x-ray, as  $\geq 10$  mm with CT scan, or  $\geq 10$  mm with calipers by clinical exam. All tumor measurements must be recorded in millimeters (or decimal fractions of centimeters). Tumor lesions that are situated in a previously irradiated area are not considered measurable.

Malignant lymph nodes: To be considered pathologically enlarged and measurable, a lymph node must be  $\geq 15$  mm in short axis when assessed by CT scan (CT scan slice thickness recommended to be no greater than 5 mm). At baseline and in follow-up, only the short axis will be measured and followed.

Non-measurable disease: All other lesions (or sites of disease), including small lesions (longest diameter  $<10$  mm or pathological lymph nodes with  $\geq 10$  to  $<15$  mm short axis), are considered non-measurable disease. Bone lesions, leptomeningeal disease, ascites, pleural/pericardial effusions, lymphangitis cutis/pulmonitis, inflammatory breast disease, and abdominal masses (not followed by CT or MRI), are considered as non-measurable.

Note: Cystic lesions that meet the criteria for radiographically defined simple cysts should not be considered as malignant lesions (neither measurable nor non-measurable) since they are, by definition, simple cysts. Cystic lesions thought to represent cystic metastases can be considered as measurable lesions, if they meet the definition of measurability described above. However, if non-cystic lesions are present in the same patient, these are preferred for selection as target lesions.

Target lesions: All measurable lesions up to a maximum of 2 lesions per organ and 5 lesions in

total, representative of all involved organs, should be identified as target lesions and recorded and measured at baseline. Target lesions should be selected on the basis of their size (lesions with the longest diameter), be representative of all involved organs, but in addition should be those that lend themselves to reproducible repeated measurements. It may be the case that, on occasion, the largest lesion does not lend itself to reproducible measurement in which

circumstance the next largest lesion which can be measured reproducibly should be selected. A sum of the diameters (longest for non-nodal lesions, short axis for nodal lesions) for all target lesions will be calculated and reported as the baseline sum diameters. If lymph nodes are to be included in the sum, then only the short axis is added into the sum. The baseline sum diameters will be used as reference to further characterize any objective tumor regression in the measurable dimension of the disease.

**Non-target lesions:** All other lesions (or sites of disease) including any measurable lesions over and above the 5 target lesions should be identified as non-target lesions and should also be recorded at baseline. Measurements of these lesions are not required, but the presence, absence, or in rare cases unequivocal progression of each should be noted throughout follow-up.

